Existing studies of SFA, like most studies of impairment-focused aphasia therapy, have provided relatively low dosages of the therapy, e.g., 3 hours per week for four weeks^[14, 15]. Participants in the research proposed below will receive much higher doses of SFA: 20 hours per week for 4 weeks. This dosage of SFA is feasible for veterans enrolling in the study: as reported in B.2 below, previous PIRATE participants have responded well to similar dosages of impairment-focused treatment and of SFA specifically. Equally importantly, this high dosage level is critical for achieving the study aims above, in several respects. First, high dosages of behavioral therapy are important for inducing significant and lasting behavioral changes. Evidence from the educational literature indicates that extended training – to and even past criterion for a learned behavior – improves short-term and long-term retention^[46-48], results in greater endurance and resistance to distraction^[49, 50], and increases generalization to related behaviors^[47, 51]. Findings from the motor therapy literature also show that high-dosage therapy, particularly when administered on an intensive schedule, leads to improved function and retention^[52-54]. Consistent with these findings, work examining the effects of constraint-induced language therapy^[30, 55, 56] suggests that massed practice and multiple repetitions of specific training activities is important for maximizing gains. Furthermore, both constraint-induced and traditional model-based treatments appear to benefit from such high-dosage administration^[57]. These findings all indicate that high dosages of aphasia therapy – involving multiple repetitions of therapy activities, training targets to or past criterion – are crucial for maximizing improvements, retaining those gains, and generalizing to untrained stimuli and other behaviors.

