impairments in type-token ratio and speech productivity. These findings illustrate the potential utility of VLSM for investigating the connection between treatment-induced changes in language performance measures (such as the PNT) and the degree of cortical and subcortical involvement, as hypothesized under Specific Aim 1.

C. Methods and Research Plan:

The proposed study will employ a within-subject repeated measures design to establish the functional relationship between amount of treatment and treatment response. We will also randomize half of the sample to a delayed treatment condition in order to control for the effects of social contact associated with PIRATE participation. Finally, we will supplement this design with between-subjects analyses designed to measure how different randomly-selected samples of participants respond to varying amounts of treatment. Study

participants will receive intensive semantically-oriented naming treatment in the context of the PIRATE program. Their response to treatment will be measured and compared across the 4-week duration of PIRATE using probes of treated and untreated stimuli as well as a standardized measure of naming performance. This comparison will address Specific Aim 2, to identify the dose-response relationship for aphasia therapy. Measures of naming gains in response to treatment will be compared across groups of participants defined in terms of their language-impairment profiles, to determine whether semantically-oriented naming treatment benefits all or only a subset of individuals with naming deficits. The study will also employ voxel-based lesion symptom mapping analyses to examine the relationship between lesion site and extent and treatment response, as well as regression analyses to examine the relationship between cognitive factors and treatment response. These analyses will together address Specific Aim 1, to identify psycholinguistic, cognitive, and neuroanatomical predictors of positive response to intensive semantically-based naming treatment.

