This design avoids the confounds present in many previous studies of treatment response. First, it holds treatment intensity constant while systematically measuring the effects of varying amounts of treatment. Second, it uses both between and within-subject design components to control for a variety of potential confounding effects, including social contact, inter-subject variability, and the passage of time. Third, it examines the relationship between psycholinguistic, cognitive, and neuroanatomical factors and treatment response. Previous studies of treatment response have examined the effects of only one of these factors in accounting for differential response to treatment.

C.1 Study participants

Potential participants will be informed of the study on the PIRATE website as well as during PIRATE candidates' initial evaluation to determine eligibility for PIRATE participation. PIRATE candidates will be informed that they may be eligible to participate in the study if they meet additional study eligibility requirements. As described below, study participants will receive up to \$1500 to defray any travel expenses incurred as part of study participation, to be pro-rated if they fail to complete all study procedures (including follow-up visits).

All study participants will be community-dwelling veterans with a positive diagnosis of aphasia and the ability to live independently and carry out activities of daily living during their PIRATE program participation. Aphasia diagnosis will be provided by the referring provider, based on performance on standardized aphasia-assessment measures such as the Comprehensive Aphasia Test (CAT), the Western Aphasia Battery, Revised (WAB-R), or the Boston Diagnostic Aphasia Exam (BDAE). Aphasia diagnosis will be verified by PIRATE staff prior to enrollment based on clinical impression and performance on the CAT, with a language modality mean T-score below the 70 being required for aphasia diagnosis. Although this criterion is more liberal than the cut-off score of 62.8 described in the CAT manual, our experience suggests that patients may score above this cut-off but nevertheless present with clinically significant naming impairments. Additional exclusionary criteria for PIRATE participation are listed in Table 5 below.

Inability to carry out activities of daily living necessary for self-care
Lack of physical independence
Significant mood or behavioral disorders
Drug or alcohol dependence

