treatment, at program exit, and at one-month follow-up. As an additional measure of within-subject control, we will also obtain baseline measures and weekly probes on the non-word repetition subtest of the PALPA. Generalization of SFA treatment to improved performance on nonword repetition is theoretically possible, but unexpected. The Philadelphia Naming Test (PNT)^[92], a standardized measure of naming performance, will be administered weekly during baseline and treatment phases of the study. In order to eliminate the possibility that observed performance gains on the PNT could be attributed to repeated exposure to the same picture stimuli, we used methods based in item response theory^[93] (IRT) to organize the 175 PNT items into seven equivalent 25-item alternate forms. We accomplished this in the following steps, using data taken from the Moss Aphasia Psycholinguistics Project Database (MAPPD)^[94], which contains item-level PNT response data collected from 254 persons with aphasia. First, we confirmed that a single underlying factor can satisfactorily account for aphasic performance on the PNT. We fit a unidimensional model to the data using NOHARM^[95], and found that fit was excellent (root mean square of the model residuals = 0.010 vs. criterion of < 0.25; Tanaka Goodness of Fit Index = 0.985 vs. criterion of >0.95 for good fit). Next, we fit the data to a 1-parameter IRT model (Rasch) for dichotomous items using WINSTEPS^[96, 97]. We found that all items obtained information-weighted mean-square statistics <1.4, suggesting adequate fit to the model^[98]. We then used the model-estimated item difficulty values to construct the seven alternate forms such that they were of equivalent overall difficulty and gave equivalent expected proportion correct scores as a function of latent naming ability. Panel A of Figure 5 shows the model predicted and empirical raw score for each alternate form as a function of Rasch-scaled latent naming ability, estimated based on the responses to the full PNT. The model curves for the seven forms are essentially identical and well-approximated by the empirical data. We then cross-validated these forms using new data from a subsample of 57 patients who were administered the PNT a second time. For these 57 patients, we computed the latent naming ability score for each alternate form and found that they adequately fit a strictly parallel test model (i.e., had equivalent means, true score variances, and error variances), $\chi^2 = 37.757$ with 32 df, $p = 0.223$. The average correlation between forms was 0.87 (min-max = 0.82-0.93). The means and standard deviations for each of the seven forms are displayed in Panel B of Figure 5.

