Study measures will be subjected to two sets of analyses which test the dose-response hypotheses relevant to Specific Aim 2. These analyses will compare the PNT scores and acquisition and generalization probe scores across the 4 weeks of PIRATE treatment, to determine the dose-response relationship and to identify the points of largest change in response to treatment. The last of the three weekly naming probes will serve as a measure of weekly acquisition and generalization performance. This will ensure that performance on PNT and naming-probe measures may be directly compared, as they will be on the same schedule.

First, the data for the PNT scores and the acquisition/generalization probes will be analyzed with a multivariate mixed model with polynomial trend contrasts. To simplify interpretation, only time points 2 through 6 (program entry through program exit) will be included in the trend analyses. These trend analyses will first test whether there is a linear relationship between time in treatment and treatment response for study measures, as predicted by Hypothesis 2a. Second, they will test whether acquisition and generalization probes show additional curvilinear relationships to time in treatment, as predicted by Hypothesis 2b. We anticipate that there will be a positive linear trend between program entry and program exit for PNT scores and for acquisition and generalization probes. This finding would indicate that the four weeks of treatment results in significant score gains. We further predict that the trend for acquisition probes will also have a significant curvilinear (quadratic or higher-order) component, consistent with decelerating improvement across the four weeks of treatment. This finding would indicate that the largest gains for specifically treated skills/items occur early in treatment, with declining gains in later weeks. Finally, we predict that the generalization probes will also demonstrate a curvilinear relationship to time, due to accelerating improvement across the four week program. This finding would indicate that the largest gains for related but untreated items occur late in treatment, emerging later than the gains for specifically treated forms.

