Second, six pairwise planned comparisons of scores across all seven consecutive measurement intervals will be carried out, using Bonferroni-corrected t-tests to maintain the familywise type-I error rate at 0.1. As predicted by Hypothesis 2a and consistent with the preliminary outcome data from PIRATE (see B.1.3 above), we anticipate that there will be a significant increase in both PNT score and acquisition/generalization probe performance for each additional one-week increment of treatment. We also predict non-significant changes between the initial evaluation and program entry and between program exit and follow-up.

In case a linear relationship is not found between time in treatment and outcome measures, additional analyses will be carried out examining the performance of different subsets of veterans. For example, veterans will be divided into groups based on their aphasia severity, since previous treatment findings have suggested that milder aphasia severity may be associated with less change on language-performance measures^[1]. Separate trend analyses will be carried out for the different severity groups, to examine whether different dose-response relationships may be observed for different aphasia groups.

In addition to these within-participant analyses examining dose-response relationships, a complementary set of between-participants analyses will be carried out, examining the effects of two versus four weeks of treatment for different randomly-selected groups of participants. It is standard practice in the dose-response literature to compare the response of groups exposed to different amounts of a therapeutic

agent, to see the incidence of positive or negative responses to the agent in the groups (e.g., frequency of remission or toxicity^[110]). These complementary between-participant analyses will simulate this comparison for the current study, providing an additional randomized-control measure of the effect of high dosage SFA on individuals with naming impairments. For these analyses, participants will be randomized to one of two groups. For half the participants, outcome measures (naming and PNT scores) will be sampled after two weeks' exposure, while for the other half, outcome measures will be sampled after the full four weeks of treatment. We anticipate that changes in study measures will be larger for the four-week group than for the two-week group.

C.3.3 Additional analyses of general language performance and connected speech

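### The supplementary two- versus four-week split randomises which scheduled score is read, not the amount of treatment, so it is not a randomised control

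*Combined protocol and SAP*

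**What the plan says.** Section C.3.2 first sets out the within-participant dose-response analyses: a mixed model with trend contrasts from program entry to program exit, and pairwise tests of consecutive intervals. It then adds a between-participant analysis. It recalls that dose-response studies usually compare groups exposed to different amounts, and continues: "These complementary between-participant analyses will simulate this comparison for the current study". The same sentence goes on to describe the analyses as "providing an additional randomized-control measure of the effect of high dosage SFA on individuals with naming impairments". The mechanism follows. For these analyses participants are randomised to two groups. One half has its naming and PNT scores read at the two-week point; the plan then says "while for the other half, outcome measures will be sampled after the full four weeks of treatment".

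The opening of section C announces the same component as "between-subjects analyses designed to measure how different randomly-selected samples of participants respond to varying amounts of treatment". A little later it credits the between- and within-subject components together with serving "to control for a variety of potential confounding effects, including social contact, inter-subject variability, and the passage of time".

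On what participants receive, section A.1.2 says that they "will receive much higher doses of SFA: 20 hours per week for 4 weeks", and section C.2 has everyone in residence for four weeks, or five in the delayed-treatment condition. On measurement, section C.2.2 says that the PNT "will be administered weekly during baseline and treatment phases of the study" and has the naming probes given three times a week. Section C.3.2 adds: "The last of the three weekly naming probes will serve as a measure of weekly acquisition and generalization performance".

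**The concern.** A randomised control for dose needs people to be allocated different amounts of treatment. Nothing in the plan shortens treatment for anyone, and both the week-2 and the week-4 score are scheduled for every participant. The allocation in section C.3.2 acts on the data set, not on the participants.

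The stake is interpretive. Dose-response is Specific Aim 2, and a positive four- versus two-week result under this label could be reported as randomised evidence that more SFA gives more gain. In the other direction, the split leaves out half of the relevant scores, so a non-significant result would say little about change between weeks 2 and 4.

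**Working it through.** The plan gives no power, effect size, SD or alpha for this split, so there is no figure to reproduce. The main check is of the design. The arithmetic only shows the cost.

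**1. What differs between the two halves**

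| Feature | Week-2 half | Week-4 half |
|---|---|---|
| Planned SFA (A.1.2) | 4 weeks | 4 weeks |
| Residence (C.2) | 4 weeks (5 if delayed) | 4 weeks (5 if delayed) |
| PNT and probe schedule (C.2.2, C.3.2) | weekly scores | weekly scores |
| Score used in the split (C.3.2) | week 2 | week 4 |

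Only the last row differs. At the week-4 reading a participant has had more SFA hours, but also more elapsed time, more residence and more probe sessions. The within-participant contrast has the same confounding.

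**2. What the split estimates**

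Random halves have the same expected scores at each week, so the split's expected value is the week-4 mean minus the week-2 mean. The paired contrast in all participants has the same target.

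As an illustration, suppose that added treatment has no effect, but that time or practice moves scores by d SD between weeks 2 and 4 (d is assumed). In simulation (10,000 runs, 25 v 25, two-sided 0.05, correlation 0.7) the split returned d as its mean estimate. It rejected in 14%, 41% and 74% of runs at d = 0.25, 0.50 and 0.75, against 4.8% at d = 0. Randomising the reading time therefore does not remove drift. The paired contrast does not remove it either. The point is that the split adds no control.

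**3. Precision**

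Input from section C.1: 50 completers, taken here as 25 v 25. Assumed: equal variance σ² of the change from entry at weeks 2 and 4, with correlation ρ between the two changes; both tests two-sided at 0.05.

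- Paired contrast, all 50: variance = 2σ²(1−ρ)/50.
- Split: variance = σ²/25 + σ²/25 = 2σ²/25.
- Ratio = (2/25) ÷ [2(1−ρ)/50] = 2/(1−ρ).

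Paired power of 80% on 49 df needs a noncentrality of 2.858. The split's noncentrality is 2.858/√ratio, on 48 df.

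| ρ (assumed) | Variance ratio | SE ratio | Split noncentrality | Split power |
|---|---|---|---|---|
| 0 | 2.0 | 1.41 | 2.02 | 51% |
| 0.5 | 4.0 | 2.00 | 1.43 | 29% |
| 0.7 | 6.7 | 2.58 | 1.11 | 19% |
| 0.9 | 20.0 | 4.47 | 0.64 | 10% |

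Averaged over all possible draws, the split estimate equals the paired estimate. The share of its variance that comes from the draw itself is therefore 1 − 1/ratio: 50% at ρ = 0, 75% at 0.5 and 95% at 0.9.

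**The case against.** The best defence is that the plan is largely open about this. It calls the analysis complementary, says that it will simulate a dose-group comparison, limits the randomisation to these analyses, and says that scores are sampled. No sample size or alpha rests on it. All of that stands and keeps the point minor. It does not rescue the label, because the sentence that says simulate goes on to claim a randomised control.

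The precision comparison can also be challenged. The paired week-4 minus week-2 contrast is not a listed test, since the planned pairwise tests cover consecutive intervals, and ρ is not in the documents. This is fair, so the result is given as a range. A single ratio of 4 would follow if entry, week-2 and week-4 scores had equal variances and equal correlations, which forces ρ = 0.5. Equal variance at entry is doubtful for the probes, whose items are chosen for low baseline accuracy.

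A reader might infer more in four ways, and the documents do not support any of them:

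- **That the split is biased.** It is unbiased for the week-4 minus week-2 difference. It is imprecise and mislabelled.
- **That Aim 2 is undermined.** The trend model and pairwise tests use the weekly scores and do not depend on the split.
- **That section C's claim to control for the passage of time is false.** That sentence credits the components jointly and never names the split. The randomised one-week delay is also a between-subject component.
- **That the delay fills the gap.** Section C.3 uses it to test one week of social contact. It does not address two versus four weeks of SFA.

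**Conclusion.** The point holds, as a minor one. The split allocates a reading time, not a dose, and adds no control beyond the within-participant comparison. The randomised-control description should go. This conclusion rests on the plan's text alone.

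The loss of precision is a factor of 2 to 20 in variance over ρ from 0 to 0.9, with power of about 51% down to 10% where the paired contrast would have 80%. Those figures depend on the assumed 25 v 25 split, equal variances, ρ and two-sided 0.05. No single value within the range can be defended from the documents.

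**What to change.** In section C.3.2, delete the randomised-control wording and replace the split with text such as: *As a supplementary analysis, the week-4 minus week-2 contrast will be estimated in all participants, with a 95% CI, from the mixed model described above, for PNT, acquisition and generalization scores. This is a non-randomised within-participant comparison.* Revise the sentence in the opening of section C that announces the between-subject analysis. The sentence there on confounding needs no edit, provided that the split is not cited as a control for the passage of time.

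If the split is kept, call it an illustrative random-subset comparison of scores at two and four weeks.

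Two cautions apply to any context given alongside the contrast:

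- The change from initial evaluation to program entry suits the PNT only. Probe items are selected because they were named correctly on fewer than two of three occasions at that evaluation (C.2.1), so their entry scores will tend to rise by regression to the mean.
- Nonword repetition may be cited as a control, with the caveat in section C.2.2 that SFA could in theory generalize to it, although this is not expected.

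The cost is wording in two places and one contrast from a model already planned, using scores already scheduled. The sponsor gives up the between-participant split announced in section C and its randomised label. Treatment and data collection do not change.
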